17.2.2 Serious Adverse Events

Serious adverse events will be summarized in terms of

- All SAEs
- All treatment emergent SAEs
- All treatment emergent SAEs leading to Death
- Local treatment emergent SAEs
- Systemic treatment emergent SAEs
- Serious TEAEs by relationship

By-subject listings will be provided for the all SAEs (treatment-emergent or not.)

17.2.3 Acute Inflammatory Reactions (AIRs)

Incidence of AIRs will be summarized.

AIR is defined as: increase of pain by 30 mm on a 100 mm VAS and a self-reported synovial fluid effusion (i.e., joint swelling) within 3 days following i.a. injection.

Synovial fluid effusions during the treatment period are reported in the subject diary by the subject answering 'Yes' to the question 'Swelling x Day1 before/after injection'. If this occurs within 3 days after injection, then the subject is classified as having a self-reported synovial fluid effusion within 3 days following i.a. injection.

Subjects are classified as experiencing an increase of pain by 30 mm on a 100 mm VAS from predose to post-dose when the following occurs within 3 days following i.a. injection:

Pain VAS (highest value recorded within 3 days following i.a.injection) $- Pain VAS (last available value before i.a.injection) \ge 30mm$

Information on pain and swelling as recorded in diary will be summarized by treatment group per injection, cycle and overall as follows:

- Number and percentage of subjects with self-reported synovial fluid effusion within 3 days following i.a. injection, for each cycle at Week 1, 2 and 3 (Yes, No);
- Number and percentage of subjects with increase of pain by 30 mm on a 100 mm VAS from pre-dose to post-dose within 3 days following i.a. injection, for each cycle at Week 1, 2 and 3 (Yes, No);
- Number and percentage of subjects experiencing an AIR, for Week 1, 2, 3 and cycle for each cycle (Yes, No).
- Number and percentage of subjects experiencing an AIR, overall (at any of the 12 injections) (Yes, No).
- Number and percentage of subjects experiencing single, multiple AIRs, or Not experiencing any AIR, overall (at any of the 12 injections).
- Number of total AIRs observed at each injection, cycle and overall (number of events, not subjects)

Fisher's exact tests will be used to test for a difference in treatment groups in the proportion of subjects experiencing AIRs. In addition, Cochran-Armitage exact trend test will be used also to evaluate whether increasing occurrences of AIRs are associated with increasing dose/injections. The number of subjects with non-missing and missing data for each item will also be presented. A by-subject listing will be provided for AIRs.

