5.3.1 Inclusion Criteria

For inclusion in the trial, all of the following inclusion criteria must be fulfilled:

1. Written informed consent given prior to any trial-related activity: subjects must understand and sign the appropriate approved Informed Consent Form(s) – one for the trial (mandatory) and one for the pharmacogenetic evaluation (optional)
2. Investigator judgment that the subject is able to comply with trial procedures and assessments
3. Primary femorotibial OA according to American College of Rheumatology (ACR) clinical and radiographic criteria (see [Appendix A](#))
4. Radiological grade of 2 or 3 according to Kellgren-Lawrence and a minimum joint space width (JSW) of ≥ 2.5 mm in the medial compartment in the target knee, obtained during screening.

Note: X-rays conducted up to 6 months prior to screening are acceptable, provided they were performed according to the specifications in the MOP and the quality is acceptable to allow confirmation of the entry criteria when read centrally.

5. Age from 40 to 85 years; of either sex
6. A history of pain due to OA in the target knee for at least 6 months
7. Pain in the target knee and/or the need for regular symptomatic treatment of knee pain with paracetamol (acetaminophen), systemic non-steroidal anti-inflammatory drugs (NSAIDs) including COX-2 selective inhibitors (coxibs), or tramadol on most days in the previous month (i.e., more than half of the days in the previous month)
8. Pain score for the target knee of 4 to 9 points in response to Question 1 of the WOMAC pain index (“how much pain have you had [in the target knee, over the past 48 hours] when walking on a flat surface?”) after washout of at least 5-half-lives of analgesic medication(s): acetaminophen, topical or oral NSAIDs, coxibs, opioids, and/or tramadol. The pain score must qualify at screening (Visit 1a for subjects not receiving analgesic medication at the time of screening and Visit 1b for subjects requiring a washout of analgesic medications) and baseline (Visit 2).
9. Women of childbearing potential (defined as any female subjects after puberty, unless postmenopausal for at least two years or surgically sterile) must use methods of contraception with a failure rate less than 1% per year when used consistently and correctly,

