6.5 Concomitant Medications and Therapies

6.5.1 Permitted Medicines

Any medications (other than those excluded by the clinical trial protocol) that are considered necessary for the subjects' welfare and will not interfere with the trial medication may be given at the Investigator's discretion.

The Investigator will record all concomitant medications taken by the subject during the trial, from the date of signature of informed consent, in the appropriate section of the CRF.

Any additional concomitant therapy that becomes necessary during the trial and any change to concomitant medication must be recorded in the corresponding section of the CRF, noting the name, dose, frequency of administration, duration, and indication of each medication.

During the screening period, all analgesic medication must be withheld for 5 half-lives before the screening (Visit 1b) and baseline WOMAC assessments. Aspirin (acetylsalicylic acid) used for cardiovascular protection does not need to be withheld, nor do antidepressants used for management of OA pain or depression.

Paracetamol (acetaminophen), NSAIDs including coxibs, and tramadol may be resumed following randomization and continued as needed during the trial, except during the brief analgesic withdrawal periods prior each study visit at which WOMAC data are obtained.

During the trial, paracetamol (acetaminophen) is recommended as rescue medication for the treatment of breakthrough pain. The dosage of acetaminophen or paracetamol that the subjects will be allowed to take per day will be defined according to the standard of care in the countries where the trial will be carried out; however, the maximum dose should not exceed 1 gram per dose and 4 grams/day. Low-dose narcotics or combination products such as paracetamol/acetaminophen and oxycodone (Percocet) may be used only as needed for more severe painful episodes. Duration of opioid use is limited to 14 days per episode. If the subject requires regular narcotic analgesia to control his/her arthritis pain, s/he should not be considered for the trial.

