- Visit 7 must be conducted within 21 to 27 weeks of the actual date of Visit 4,
- Visit 12 must be conducted within 21 to 27 weeks of the actual date of Visit 9, and
- Visit 17 must be conducted within 21 to 27 weeks of the actual date of Visit 14

Allowable intervals for other visits:

During the DBPC treatment phase, visits may take place within ± 4 days of the planned day. This interval allowance applies to Visits 5, 6, 10, 11, 15, 16, 20, and 21.

Extended follow-up visits may take place within ± 21 days of the planned day. This interval allowance applies from Visit 22 (EF1) through Visit 28 (EF6).

Allowable intervals for X-rays and MRIs:

At time points where IMP administration is scheduled, X-rays and MRIs may be performed up to 3 days before the IMP administration.

During the DBPC phase, at time points where there is no IMP administration scheduled, X-rays and MRIs may be performed within ± 4 days of the planned day.

During the extended follow up phase, at time points when there is no IMP administration scheduled, X-rays and MRIs may be performed within ± 7 days of the planned day.

Pain Medication Washout

Subjects will be requested to discontinue the intake of all pain medications for 5 half-lives before a visit involving completion of the WOMAC. At least 3 days before each such visit, subjects will be contacted by phone to remind them of this requirement.

Aspirin (acetylsalicylic acid) used for cardiovascular protection does not need to be withheld, nor do antidepressants used for management of OA pain or depression.

Subject Questionnaires

At visits involving completion of subject questionnaires (WOMAC, PGA, KOOS QOL, KOOS Symptom Index, PGIC, NRS pain score in the target and contralateral knee, MOS SF-36, pain in other joints, and ICOAP), these questionnaires must be completed before any other trial procedures are performed. The WOMAC should be completed first.

Subject Diaries

Subjects will receive diaries at each visit for recording of the following information:

- Any adverse reaction occurring between trial visits and any concomitant medications used, with particular attention to the use of NSAIDs, coxibs, and any other pain medications
- Maximum pain level (using a 100-mm VAS) and presence or absence of joint swelling, to be recorded once daily on the day before each IMP injection and on each of the 3 days following an IMP injection.

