 - Diaries given at the visit before the beginning of a treatment cycle (e.g., screening or Week 12/Visit 6) will collect pain and swelling information for the day before the next visit. Telephone contacts concerning the need to withhold pain medications before the next visit will include a reminder to complete this diary information.

- Diaries given at visits where the first and second doses of a cycle are administered will collect pain and swelling information for the 3 days after the injection and for the day before the next visit.
- Diaries given at visits where the last dose of a cycle is administered will collect pain and swelling information for the 3 days after the injection.
- Diaries given at all other visits will collect adverse reactions and concomitant medications only.

Different diaries will be dispensed, depending on the data to be completed prior to the next visit. Completed diaries will be collected and reviewed at each visit, and information will be transcribed to the CRFs (following medical review in case of AE or concomitant medication information).

Pharmacogenetic Analysis

All subjects who are enrolled in the trial will be eligible to participate in an optional PGt analysis (except in countries where collection of PGt samples is not allowed; the analysis is described in Section 7.6.3). Participation is optional, and the subjects who choose to participate will need to sign a specific PGt ICF (see Section 9.2).

For consenting subjects, a single blood sample will be collected for PGt analysis. This sample can be obtained at any trial visit, preferably at baseline.

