7.1.3 Double-Blind Placebo-Controlled Treatment Phase (Visits 2 to 22)

The duration of the DBPC treatment phase will be 2 years (104 weeks). Trial visits during this phase are outlined in [Table 2](#), and details of the procedures to be performed are presented in [Appendix E](#).

Table 2 Trial Visits during DBPC Treatment Phase

Visit Number	Week*	Treatment	Visit Name or Type
2	0	X	Baseline – Major Efficacy
3	1	X	
4	2	X	
5	3		
6	12		Minor Efficacy
7	26	X	Major Efficacy
8	27	X	
9	28	X	
10	29		
11	38		Minor Efficacy
12	52	X	Major Efficacy
13	53	X	
14	54	X	
15	55		
16	64		Minor Efficacy
17	78	X	Major Efficacy
18	79	X	
19	80	X	
20	81		
21	90		Minor Efficacy
22	104		Major Efficacy

* Relative to randomization and initiation of therapy at Week 0. Assessments performed at “major” and “minor” efficacy visits are described in Sections 7.1.3.3 and 7.1.3.4 respectively.

Subject eligibility for the trial will be confirmed at the baseline visit (Week 0/Visit 2; see Section 7.1.3.1) based on scores for Question 1 of the WOMAC pain index at screening and baseline (see Section 5.4). Eligible subjects will then be randomized and the first i.a. injection of IMP will be administered.

I.a. injections of the IMP will be administered at the baseline visit (Week 0/Visit 2) and at the visits identified in Section 7.1.3.2.

Major efficacy assessments will take place at intervals of 6 months, at the beginning of each treatment cycle and at the end of the DBPC treatment phase (Week 104/Visit 22; see Section 7.1.3.3).

Minor efficacy assessments will also take place at intervals of 6 months, occurring 9 weeks after the end of each treatment cycle (see Section 7.1.3.4).

Subjects will be requested to discontinue the intake of all pain medications for 5 half-lives before a visit involving completion of the WOMAC (see Sections 5.4 and 7.1.2). At least 3 days before each such visit, subjects will be contacted by phone to remind them of this requirement. When

the upcoming visit includes injection of IMP, this phone contact will include a reminder to complete trial diary information about target knee pain and swelling for the day before the visit.

Vital signs measurement (see Section 7.4.4) and review of AEs and concomitant medications (see Sections 7.4.1 and 6.5) will be performed at all DBPC treatment phase visits.

For women of childbearing potential, urine pregnancy tests will be performed before dosing on each treatment day (see Section 7.1.3.3).

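### The AIR pain rule in SAP 17.2.3 sets no time limit on the pre-dose VAS, and at 4 of 12 injections that value may also be raised by analgesic washout

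*SAP*

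**What the plan says.** SAP 17.2.3 defines an AIR as "increase of pain by 30 mm on a 100 mm VAS and a self-reported synovial fluid effusion" within three days of an intra-articular injection. The pain part is the highest VAS in those three days minus "Pain VAS (last available value before i.a.injection", and the difference must be at least 30 mm. The section gives no limit on the age of the pre-dose value, no rule for pre-dose values near the top of the scale, and no allowance for analgesic use.

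Protocol 7.1.1 (Subject Diaries) says maximum pain and swelling are "to be recorded once daily on the day before each IMP injection and on each of the 3 days following an IMP injection". Between cycles, the diaries ask for pain and swelling only on the day before the next cycle starts.

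Protocol 7.1.1 (Pain Medication Washout) adds: "Subjects will be requested to discontinue the intake of all pain medications for 5 half-lives before a visit involving completion of the WOMAC". Protocol 7.1.3 places WOMAC visits at the start of each cycle: "Major efficacy assessments will take place at intervals of 6 months, at the beginning of each treatment cycle". The same phone call covers both tasks: "Telephone contacts concerning the need to withhold pain medications before the next visit will include a reminder to complete this diary information". Of paracetamol, NSAIDs and tramadol, Protocol 6.5.1 says that they "may be resumed following randomization and continued as needed during the trial, except during the brief analgesic withdrawal periods prior each study visit". The visits meant there are those with a WOMAC.

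**The concern.** AIR incidence is a listed safety endpoint and the pre-defined adverse event of special interest (Protocol 7.4.1.1). The background section of the Protocol reports slightly more AIRs on active treatment in the proof-of-concept trial, with no evident dose-response. SAP 17.2.3 tabulates AIRs by injection, cycle and overall, and applies Fisher's exact tests and a trend test. Whether an injection counts as an AIR depends on one subtraction, so the subtracted value needs to describe the knee just before that injection and under comparable conditions.

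There are three weaknesses:

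- **Carry-back.** When the day-before entry is missing, the rule reaches back without limit.
- **Washout.** At first injections the pre-dose value may be off analgesia and the post-dose values on it. At second and third injections no washout is required.
- **Ceiling.** A high pre-dose value leaves no room for a 30-mm rise.

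The first can produce a wrong AIR classification. The second can distort the comparison of first with later injections, which the by-injection tables invite. The third lowers sensitivity at any injection where pre-dose pain is high.

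**Working it through.** **1. Which injections follow a washout.** The SAP's own count is 12 injections: 4 cycles × 3 = 12. From Protocol Table 2 and Appendix E:

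- Injection visits: 2, 3, 4, 7, 8, 9, 12, 13, 14, 17, 18, 19.
- WOMAC visits from Visit 2 to Visit 22: 2, 6, 7, 11, 12, 16, 17, 21, 22.
- Both: 2, 7, 12, 17 (Weeks 0, 26, 52, 78), so 4/12 = 33%, always the first injection of a cycle.

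**2. Age of the carried-back value.** Protocol 7.1.1 sets 7 days between injections within a cycle (6 to 9 allowed) and 24 weeks from the last injection of one cycle to the first of the next (21 to 27 allowed). The last VAS before a missing day-before entry is day 3 after the previous injection.

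| Injection | Age of fallback value | Allowed range |
|---|---|---|
| Second or third of a cycle | 7 − 3 = 4 days | 3 to 6 days |
| First of cycles 2 to 4 | 24×7 − 3 = 165 days (23.6 weeks) | 144 to 186 days |
| First of cycle 1 | no earlier diary VAS | – |

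If the carried value exceeds the true day-before value by d mm, the subject needs a rise of 30 + d mm; if it is lower, less than 30 mm is enough. At second and third injections d may be positive because day-3 pain can itself be reaction pain. For the 24-week-old value the sign of d is unpredictable.

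**3. Ceiling.** The largest possible rise is 100 − pre-dose. At 70 mm it is 30 mm (can qualify); at 71 mm it is 29 mm (cannot). This holds at all 12 injections and is assessed afresh at each.

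**4. Washout.** If washout raises the pre-dose value by s mm and later values are under analgesia, the required rise is 30 + s mm on the subject's usual scale. The documents give no VAS distribution, no s and no share of analgesic users, so what follows is an illustration. Assumptions: on-analgesic VAS mean 50, SD 20; a true reaction adds mean 45, SD 15; values limited to 0–100; swelling always reported.

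| Shift s, applied to every subject | True reactions meeting 30 mm | Pre-dose above 70 mm |
|---|---|---|
| 0 mm | 71% | 16% |
| 10 mm | 44% | 31% |
| 20 mm | 19% | 50% |

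If only 30% of subjects are shifted by 10 mm, detection is 0.7×71 + 0.3×44 = 63%. For non-users it stays at 71%.

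**5. Effect on the subject-level count.** Any AIR = 1 − (1 − r×0.71)^8 × (1 − r×D)^4, with r an assumed independent reaction risk per injection and D the detection at first injections.

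| r | No shift (D = 0.71) | 30% shifted by 10 mm (D = 0.63) | All shifted by 10 mm (D = 0.44) |
|---|---|---|---|
| 2% | 15.8% | 15.2% | 13.9% |
| 5% | 35.2% | 34.1% | 31.5% |

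**6. How much of the day before is washed out.** Assume a 09:00 visit; the day before then runs from 33 to 9 hours earlier. Share covered by the minimum washout = (5 × half-life − 9)/24, limited to 0–1. A 2-hour half-life gives 4%, 3 hours 25%, 6 hours 88%, and 6.6 hours or more 100%.

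**The case against.** The case for leaving the rule alone has real force.

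- **The washout effect may be small.** Pain or regular treatment each suffices under inclusion criterion 7, so analgesic users could be a minority. For short half-life drugs the washout may cover little of the day before. Eight of 12 injections have no washout. This stands, and it is why the effect can only be called possible.
- **A bias runs the other way.** The rule compares one pre-dose daily maximum with the highest of three post-dose daily maxima. Without any reaction, the highest of three independent days exceeds a single day by about 0.85 SD: 4 to 13 mm for an assumed day-to-day SD of 5 to 15 mm. This also stands. The net direction for overall incidence is therefore undetermined, and a reader should not infer that every incidence is lowered. It applies at all 12 injections, so it does not remove the first-versus-later contrast.
- **No bias between arms is shown.** Washout and scoring are the same in every arm. A reader might infer dilution of the sprifermin–placebo comparison towards no signal. Equal loss of sensitivity shrinks a risk difference but leaves the risk ratio about unchanged, and the documents support no stronger statement.
- **High pain does not bar a subject for good.** Entry requires "Pain score for the target knee of 4 to 9 points in response to Question 1 of the WOMAC pain index" after washout, and from that one might infer that subjects scoring 8 or 9 can never have an AIR. That item has a different scale and recall period from the diary VAS, the pre-dose value is retaken each time, and the subject-level count is over any of the 12 injections.
- **Other displays exist.** SAP 17.2.3 already tabulates swelling alone, pain increase alone and missing data. Local adverse events and injection site reactions are reported without a VAS threshold. These help, but none identifies carried-back values, ceiling cases or washout effects.

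**Conclusion.** The unlimited carry-back is a definite gap: as written, the SAP can score an AIR against pain 4 days old that may itself be a reaction, or pain about 24 weeks old. How often this happens depends on diary completeness, which the documents do not give.

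The washout point holds as a possibility. At 4 of 12 injections, AIRs may be under-detected in analgesic users relative to second and third injections. In the illustration, detection of true reactions at those injections runs from 71% (no shift) to 63% (30% of subjects shifted by 10 mm) to 44% (all shifted by 10 mm). At a 2% reaction risk per injection, the any-AIR figure moves only from 15.8% to 15.2% or 13.9%. All of these rest on assumed VAS distributions.

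The ceiling is exact but applies per injection: above 70 mm, the pain criterion cannot be met at that injection. The documents do not support a claim of between-arm bias or of a certain under-count.

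**What to change.** Keep the protocol AIR definition as the main one and amend SAP 17.2.3, using data already collected:

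1. Replace the last available value with the diary VAS for the day before that injection. When that entry is absent, count the pain criterion as missing for that injection. The cost is slightly fewer evaluable injections. Because an AIR needs both parts, an injection with swelling recorded as absent on all three days can still be scored as no AIR.
2. Keep injections with a pre-dose VAS above 70 mm in the main analysis, but report their number by arm and injection.
3. As a supportive summary only, show AIRs for first versus second and third injections, split by diary-recorded analgesic use, beside the swelling-alone table already planned. Use after an injection may itself be a response to a reaction, so this split is descriptive.

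Two further steps are best avoided. Excluding injections above 70 mm would condition on a value that, after the first injection, may already reflect a drug reaction. A looser definition accepting any VAS increase would count a 1-mm rise as an AIR.

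The whole change is SAP wording, one added count and one added table.

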In the DBPC treatment phase, all subjects will receive 4 cycles of treatment with the IMP (sprifermin or matching placebo) at intervals of 6 months. Each cycle will consist of 3 once-weekly i.a. injections over a period of 3 consecutive weeks.

The DBPC treatment phase will begin at the baseline visit (Week 0/Visit 2), when eligibility will be confirmed, subjects will be randomized, and the first IMP injection will be administered.

Subjects will be randomized in equal allocation to one of the following treatment groups, as shown in [Figure 1](#) (randomization is described in Section 6.3).

- 4 cycles of sprifermin (100 mcg per injection)
- 2 cycles of sprifermin (100 mcg per injection) alternating with 2 cycles of placebo
- 4 cycles of sprifermin (30 mcg per injection)
- 2 cycles of sprifermin (30 mcg per injection) alternating with 2 cycles of placebo
- 4 cycles of placebo

The last of the four cycles of 3 injections of IMP will be given on Week 78/Visit 17, and the last dose of IMP is scheduled to be administered at Week 80/Visit 19. IMP administration for each treatment group is summarized in [Table 1](#), Section 6.2.

Major efficacy assessments will take place at intervals of 6 months, on the first day of each treatment cycle and at the end of the DBPC treatment phase (Week 104/Visit 22).

Minor efficacy assessments will also take place at intervals of 6 months, occurring 9 weeks after the end of each treatment cycle.

Details of DBPC treatment phase visits are presented in Section 7.1.3.

Efficacy assessments will include MRI and X-ray of the target knee, the WOMAC, the 20-meter walk test, and the Patient's Global Assessment of disease impact (PGA). The Knee Injury and Osteoarthritis Outcome Score QOL subscale (KOOS QOL) and the Medical Outcomes Study Short Form-36 General Health Survey (MOS SF-36) will be assessed for exploratory analysis of treatment effect on health-related QOL. The NRS will be used to explore treatment effect on worst pain in the past 24 hours in the target knee. The Measure of Intermittent and Constant Osteoarthritis Pain (ICOAP) and the KOOS Symptom Index questionnaires will be used to explore treatment effect on OA-related symptomatology in the target knee. The NRS pain scale

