6.2 Dosage and Administration

In the DBPC treatment phase, all subjects will receive 4 cycles of treatment with the IMP (sprifermin or matching placebo) at intervals of 6 months. Each cycle will consist of 3 once-weekly i.a. injections over a period of 3 consecutive weeks.

IMP administration for each treatment group is summarized in Table 1.

Table 1 Drug Administration Diagram

	Cycle 1 W0, W1, W2	Cycle 2 W26, W27, W28	Cycle 3 W52, W53, W54	Cycle 4 W78, W79, W80	Dose per cycle	Total dose
Group 1	100 mcg	100 mcg	100 mcg	100 mcg	300 mcg	1200 mcg
Group 2	100 mcg	Placebo	100 mcg	Placebo	300 mcg/placebo	600 mcg
Group 3	30 mcg	30 mcg	30 mcg	30 mcg	90 mcg	360 mcg
Group 4	30 mcg	Placebo	30 mcg	Placebo	90 mcg/placebo	180 mcg
Group 5	Placebo	Placebo	Placebo	Placebo	Placebo	Placebo

Each cycle consists of 3 once-weekly i.a. injections of the specified dose over 3 consecutive weeks.

The central randomization service’s interactive voice response system (IVRS) will be used to randomize subjects and to assign a blinded treatment kit at each treatment visit, as described in Section 6.3.

Each treatment kit will include materials for a single injection.

All kits will include 1 glass vial of IMP (sprifermin or placebo) and 1 glass ampule of sterile saline solution for injection (2 mL per ampule) to be used for reconstitution (see Section 6.6).

Instructions for reconstitution are provided in the MOP. Once reconstituted, the IMP may remain in the syringe for up to 2 hours prior to administration.

The Investigator or a suitably qualified designee will administer the IMP. The exact time of IMP administration will be documented in the CRF.

I.a. administration of the IMP will be guided through the use of ultrasound to ensure delivery into the joint space. Detailed instructions for injection are provided in the MOP.

Before injecting the IMP solution, an aspiration of the synovial fluid for local PK and biomarker analysis will be performed as part of the i.a. injection procedure, using the same needle that will be used for IMP injection. If possible, up to 2.5 mL should be collected (instructions for sample handling are provided in the MOP).

The volume of IMP solution to be injected will be 2 mL. The needle for injection will be flushed with 0.5 mL saline to make sure the entire dose has been injected (thus, the total volume injected will be 2.5 mL).

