- Change from baseline in serum, urine, and synovial markers associated with administration of the compound
- Baseline biochemical biomarkers and/or genetic markers associated with response to treatment or disease progression (response assessed by MRI, X-ray and/or questionnaire)
- Changes in MRI outcomes, WOMAC scores, 20-meter walk test, PGA, PGIC, JSW, OMERACT-OARSI responder rate, KOOS QOL, KOOS Symptom Index, MOS SF-36, NRS pain score in the target and contralateral knee, presence of pain in other joints, ICOAP, safety laboratory values, and vital signs over the extended follow-up period and nature, incidence and severity of local and systemic AEs during the extended follow-up period (to be summarized descriptively)
- Relationship between dosing (dose and regimen), cartilage structures, and clinical scores as a function of time

Trial Design	This is a multicenter, randomized, double-blind, placebo-controlled, parallel-group Phase II trial of sprifermin administered i.a. in subjects with primary OA of the knee and Kellgren-Lawrence (KL) grade 2 or 3.
	The trial consists of a screening period lasting up to 42 days, a 2-year (104-week) double-blind placebo-controlled (DBPC) treatment phase, which will start at randomization (Week 0/Visit 2) and a 3-year extended follow-up phase. Please see table 5 and 6 (Appendix E) in the clinical trial protocol. Please see below for specification of dose groups (Trial Product).
Number of Subjects	The trial will randomize approximately 545 subjects (109 per treatment group).
Trial Product	Sprifermin (also known as: recombinant human fibroblast growth factor 18 [rhFGF-18]; AS902330) 30 mcg or 100 mcg, administered intra-articularly (i.a.).
	Subjects will receive 4 cycles of treatment (each consisting of 3 once-weekly i.a. injections over 3 consecutive weeks) at intervals of 6 months.
	Subjects will be randomized in equal allocation to one of 5 treatment groups:
	• 4 cycles of sprifermin (100 mcg per injection, total dose 1200 mcg)
	• 2 cycles of sprifermin (100 mcg per injection) alternating with 2 cycles of placebo (total dose 600 mcg)
	• 4 cycles of sprifermin (30 mcg per injection, total dose 360 mcg)
	• 2 cycles of sprifermin (30 mcg per injection) alternating with 2 cycles of placebo (total dose 180 mcg)
	• 4 cycles of placebo (total dose 0 mcg)
Treatment and Trial Duration	Planned treatment duration is 2 years.
	Follow-up duration is 3 years.

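### Acute inflammatory reactions (AIRs) are tested only between arms, although half the injections in the two alternating arms are placebo; no estimate or test by injection content is planned

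*SAP*

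**What the plan says.** SAP 17.2.3 defines an AIR as a pain increase of 30 mm on the 100 mm scale together with self-reported swelling, both within 3 days after an injection. The pain increase is measured from the last value before that injection.

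Two inferential analyses follow. The first is "Fisher's exact tests will be used to test for a difference in treatment groups in the proportion of subjects experiencing AIRs". The second is that a "Cochran-Armitage exact trend test will be used also to evaluate whether increasing occurrences of AIRs are associated with increasing dose/injections". SAP section 11 (Summary Statistics) makes this trend test the one exception to two-sided testing. The SAP does not say whether either test is run overall or per cycle, and it gives no trend scores.

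The descriptive part is fuller: "Information on pain and swelling as recorded in diary will be summarized by treatment group per injection, cycle and overall as follows". It covers subjects and event counts and includes "Number and percentage of subjects experiencing an AIR, overall (at any of the 12 injections) (Yes, No").

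On treatment, Protocol 6.2 states "Each cycle will consist of 3 once-weekly i.a. injections over a period of 3 consecutive weeks". Two of the four sprifermin groups in Protocol 5.1 are "2 cycles of sprifermin (100 mcg per injection) alternating with 2 cycles of placebo" and "2 cycles of sprifermin (30 mcg per injection) alternating with 2 cycles of placebo". Table 1 of the protocol puts the placebo cycles of these groups at cycles 2 and 4. SAP section 17 groups subjects as treated for safety.

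**The concern.** The exposure relevant to an AIR is the content of the injection that preceded it. Over 12 injections, a by-arm subject proportion mixes sprifermin and placebo reactions in the two alternating arms. In the per-cycle tables, reactions to placebo in cycles 2 and 4 appear under a sprifermin heading.

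The phrase dose/injections adds an ambiguity. By total dose the arms run 0, 180, 360, 600, 1200 mcg, but in that order the number of active injections runs 0, 6, 12, 6, 12. These two orderings lead to different trend tests.

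AIR incidence is a named safety endpoint (Protocol 8.3.3). Protocol section 3 reports slightly more AIRs on active treatment in the earlier proof-of-concept trial, with no dose-response evident. An arm-level dose trend is weak for exactly that pattern.

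**Working it through.** **Design figures.** The plan gives no AIR rate or AIR power to reproduce. Its dose and size figures do reproduce. In the alternating arms 6 × 100 = 600 mcg and 6 × 30 = 180 mcg, as in Table 1. For size, 76 / 0.7 = 108.6, hence 109 per arm and 545 in total.

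**Planned injections by content**, at 109 per arm:
- placebo: 109 × (12 + 6 + 6) = 2616, twice the 109 × 12 = 1308 of the placebo arm alone
- 30 mcg: 109 × (12 + 6) = 1962
- 100 mcg: 109 × (12 + 6) = 1962

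**Proportion with any AIR.** With assumed per-injection risks p0 (placebo) and p1 (active) and independent injections, P(any AIR) = 1 − (1 − p0)^n0 × (1 − p1)^n1.

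| Arm (total dose) | n0, n1 | Rates 1% / 2% / 2% | Rates 1% / 1.5% / 3% |
|---|---|---|---|
| Placebo (0) | 12, 0 | 11.4% | 11.4% |
| 30 mcg, 2 cycles (180) | 6, 6 | 16.6% | 14.0% |
| 30 mcg, 4 cycles (360) | 0, 12 | 21.5% | 16.6% |
| 100 mcg, 2 cycles (600) | 6, 6 | 16.6% | 21.6% |
| 100 mcg, 4 cycles (1200) | 0, 12 | 21.5% | 30.6% |

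Rates are for placebo / 30 mcg / 100 mcg injections. If the two strengths carry the same risk, the pattern over total dose is not monotone. If risk rises with strength, it can be monotone, as in the last column.

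**Dilution.** Write a = (1 − p0)^6 and b = (1 − p1)^6. The excess over placebo is a(a − b) in an alternating arm and (a − b)(a + b) in the four-cycle arm of the same strength. The share kept is a / (a + b). At 1% and 2%, this is 0.9415 / (0.9415 + 0.8858) = 0.515. Over placebo rates of 0.25% to 1% and risk ratios up to 3 it is 0.50 to 0.53. At 3% and a ratio of 5 it reaches 0.69. On expected event counts it is exactly 0.50.

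**Power.** Simulation with 109 per arm, no dropout and one-sided 5%. Ranges run from gamma subject frailty of variance 1 to no frailty. The trend is the normal-approximation Cochran-Armitage test on any AIR over 12 injections, with equally spaced scores. The injection contrast is 100 mcg versus placebo from a cycle-adjusted, subject-clustered logistic model with three content levels.

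| Assumed rates | Arm trend | 100 mcg vs placebo injections |
|---|---|---|
| 1% / 2% / 2% | 49–56% | 77–82% |
| 1% / 1.25% / 2% | 65–72% | 80–82% |
| 1% / 1.5% / 3% | 97–99% | over 99% |

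Under no effect both reject about 5–6% of the time. Repeat runs move the figures by a few points.

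**Scores.** At 1% / 2% / 2% without frailty, one-sided trend power is about 48–50% with total dose as the score, about 56% with equal spacing, and about 77% with the number of active injections (0, 6, 12, 6, 12).

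**Pairwise, two-sided, 1% / 2% / 2%.** The 100 mcg four-cycle arm versus placebo has about 46–52% power, and the 100 mcg alternating arm about 18–21%. The injection contrast, also two-sided, has about 70–77%.

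**The case against.** The strongest reply is that little is lost. AIRs are tabulated by arm per injection and per cycle, as subjects and as events. Planned content is fixed by arm and cycle, so a reader can add up the cells. Cycle 1 is already a clean randomized comparison. That stands: a reader might infer that the plan discards the sprifermin-versus-placebo comparison, and the documents do not support this. What is missing is a prespecified estimate or test.

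Second, the planned tests may serve well. The trend test is one-sided, the four-cycle arms are undiluted, and at 1% / 1.5% / 3% the trend already has about 97–99% power. If Fisher's tests are run per cycle, cycles 1 and 3 are undiluted too. That also stands, so one cannot say that the tests would generally miss a real effect. But the SAP does not fix the level or the scores.

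Third, a by-content analysis is no automatic gain. A simple active-versus-placebo split can lose to the trend when risk depends on strength (about 67% versus 74% at 1% / 1.25% / 2%, one-sided, no frailty). Keeping three content levels avoids this.

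Fourth, the alternation has a fixed order, so content within those arms is confounded with cycle, and later contrasts assume no carry-over. The placebo arm supplies a same-cycle reference, but carry-over remains an assumption. This argues against making the pooled model the main comparison.

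As-treated grouping does not remove the problem, because the placebo cycles are part of the planned regimen.

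**Conclusion.** The concern holds as a gap in the AIR analysis. The tests compare whole arms, two of which are half placebo by injection, and no estimate or test uses the content of the injection. The 6-of-12 split and the missing analysis follow from the documents. The halving of the excess follows by arithmetic and is approximate except at low rates.

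The power gain is illustrative only, because every AIR rate is assumed. It is material if both strengths carry similar risk (about 49–56% versus 77–82%) and close to nil if risk rises steeply with strength. With no dropout modelled, against the plan's 30% at two years, absolute powers are optimistic for both approaches.

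A reader might also conclude that the by-arm tests are invalid or should be replaced. The documents do not support that: the by-arm tests compare regimens, which is a legitimate question.

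**What to change.** In SAP 17.2.3, keep the by-arm analyses and add:

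1. A table by actual injection content (placebo, 30 mcg, 100 mcg) giving injections, AIRs, rate and 95% CI.
2. A logistic model clustered by subject, with content (three levels), cycle and injection number within cycle as factors, reporting each strength against placebo with a 95% CI.
3. The same comparison in cycle 1 only, as a check on carry-over. At full enrolment this has 109 × 3 = 327 placebo injections and 218 × 3 = 654 of each strength.
4. The level (overall or per cycle) of the Fisher and trend tests, and the trend scores.

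The cost is one table and one model. The diaries already record pain and swelling around each injection (Protocol 7.1.1). The price in assumptions is that an earlier active cycle does not alter the 3-day reaction to a placebo injection about 24 weeks later, which item 3 helps to examine.
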